#### 6.4.4 Visit T4 (Week 10)

The following procedures will be performed at Visit T4 (Week 10/Day 71 ±3 days):

- Perform symptom directed physical examination;
- Record vital signs and weight;
- Perform urine pregnancy test (for women of child-bearing potential only);
- Obtain blood sample for the following:
  - Safety chemistry panel, coagulation, and hematology;
  - Fasting lipid panel, LDL-C ultracentrifugation, apolipoproteins;
  - hsCRP, IL-6, SAA, and fibrinogen;
  - Reserve serum and PK plasma samples;

- Perform 12-lead ECG;
- Assess and document study drug compliance;
- Explain importance of continued adherence to a stable, heart-healthy diet and limited alcohol intake;
- Collect subject dose diary;
- Distribute subject dose diary;
- Assess adverse events and update concomitant medications; and
- Administer study drug (subjects will self-dose).

#### 6.4.5 Visit T5 (Week 12)

The following procedures will be performed at Visit T5 (Week 12/Study Day 85 [can be performed up to 3 days prior to Study Day 85, but not after Study Day 85]):

- Perform full physical examination;
- Record vital signs and weight;
- Collect urine sample;
- Perform serum pregnancy test (for women of child-bearing potential only);
- Obtain blood sample for the following:
  - Safety chemistry panel (clinically significant abnormal creatinine results at Week 12 will also be followed-up 2 weeks ( $\pm 3$  days) after the last dose of study drug in addition to the 4 week ( $\pm 3$  days) Follow-up Visit), coagulation, and hematology;
  - Fasting lipid panel, LDL-C ultracentrifugation, and apolipoproteins;
  - Fasting lipoprotein size and number (NMR);
  - Fasting insulin and FPG;
  - HbA1c;
  - hsCRP, IL-6, SAA, ANGPTL4, adiponectin, fibrinogen;
  - Cystatin-C;
  - Reserve serum and PK plasma samples;
- Perform 12-lead ECG;
- Assess and document study drug compliance;
- Collect subject dose diary;
- Assess adverse events and update concomitant medications.

## **6.5 Follow-up Visit (Week 16)**

The Follow-up Visit will be conducted as a telephone call 4 weeks ( $\pm 3$  days) after the last dose of study drug, unless the subject requires a site visit due to an abnormal result at Week 12 (or the ET Visit, if applicable) or an ongoing treatment-related adverse event.

The following procedures will be performed at the Follow-up Visit (Week 16  $\pm 3$  days):

- Perform symptom-directed physical examination (only for subjects who had an abnormal result at Week 12 [or the ET Visit, if applicable] or an ongoing treatment-related adverse event);
- Collect urine sample for urinalysis including urine protein:creatinine ratio, albumin:creatinine ratio and NGAL (only for subjects who had an abnormal result at Week 16 [or the ET Visit, if applicable] or an ongoing treatment-related adverse event);
- Obtain blood sample for safety chemistry panel, cystatin-C, coagulation, and hematology (only for subjects who had an abnormal result at Week 12 [or the ET Visit, if applicable] or an ongoing treatment-related adverse event); and
- Assess adverse events and update concomitant medications.

## **6.6 Early Termination Visit and Withdrawal Procedures**

For subjects who are withdrawn from the study prior to completion, the following procedures will be performed at the ET Visit:

- Perform full physical examination;
- Record vital signs and weight and waist circumference;
- Collect urine sample;
- Perform serum pregnancy test (for women of child-bearing potential only);
- Obtain blood sample for the following:
  - Safety chemistry panel, coagulation, and hematology;
  - Fasting lipid panel and apolipoproteins;
  - Fasting lipoprotein size and number (NMR);
  - Fasting insulin, and FPG;
  - HbA1c;
  - hsCRP, IL-6, SAA, ANGPTL4, adiponectin, and fibrinogen;
  - Cystatin-C;
  - Reserve serum and PK plasma samples;
- Perform 12-lead ECG;
- Assess and document study drug compliance;

- Collect subject dose diary; and
- Assess adverse events and update concomitant medications.

## 7 EFFICACY ASSESSMENTS

The following efficacy assessments will be measured in order to obtain the primary, secondary, and exploratory endpoints:

- Fasting TG, TC, HDL-C, non-HDL-C, VLDL-C at baseline, Week 2, Week 6, Week 10 and Week 12;
- Fasting LDL-C (ultracentrifugation), LDL-TG, VLDL-TG, HDL-TG at baseline, Week 10 and Week 12;
- Fasting total apolipoprotein B (ApoB), ApoA-I, ApoA-II, ApoA-V, ApoC-II, ApoC-III, and ApoE at baseline, Week 10 and Week 12;
- Fasting lipoprotein size and number (NMR), adiponectin, ANGPTL4 at baseline and Week 12;
- hsCRP, IL-6, SAA and fibrinogen at baseline, Week 10 and Week 12;
- **Cl** [REDACTED]
- [REDACTED]

## 8 SAFETY ASSESSMENTS

### 8.1 Adverse Events

An adverse event is defined as any untoward medical occurrence in a clinical investigation subject administered a pharmaceutical product, which does not necessarily have a causal relationship with this treatment. An adverse event can therefore be any unfavorable and/or unintended sign (including an abnormal laboratory finding), symptom, or disease temporally associated with the use of an investigational medicinal product, whether or not related to the investigational medicinal product. All adverse events, including observed or volunteered problems, complaints, or symptoms, are to be recorded on the appropriate eCRF.

Adverse events, which include abnormal and clinically significant clinical laboratory test variables, will be monitored and documented from the time of first dose of study drug (Study Day 1) until study participation is complete (the Follow-up Visit). Subjects should be instructed to report any adverse event that they experience to the Investigator. Beginning with the signing of the informed consent until the time of the first dose of study drug (Study Day 1), Investigators should make updates to medical history and record any pre-existing medical condition or signs or symptoms that changes in severity, frequency, or seriousness in the medical history. Serious adverse events that occur prior to the first dose of study drug (Study Day 1) should be reported as an update to medical history as well as be reported on the appropriate adverse event eCRF. Beginning with the first dose of study drug (Study Day 1), Investigators should make an assessment for adverse events at each visit and record all adverse events, non-serious and serious, on the appropriate adverse event eCRF.

Wherever possible, a specific disease or syndrome rather than individual associated signs and symptoms should be identified by the Investigator and recorded on the eCRF. However, if an observed or reported sign or symptom is not considered a component of a specific disease or syndrome by the Investigator, it should be recorded as a separate adverse event on the eCRF. Additionally, the condition that led to a medical or surgical procedure (e.g., surgery, endoscopy, tooth extraction, or transfusion) should be recorded as an adverse event, not the procedure. Concomitant procedures should be recorded as such on the appropriate eCRF.

Any medical condition already present prior to the subject taking the first dose of study drug (Study Day 1) should be reported in the medical history. Any SAEs occurring prior to the first dose of study drug (Study Day 1) should be reported as an update to medical history as well as an adverse event. Any pre-existing medical condition or signs or symptoms that changes in severity, frequency, or seriousness after the subject takes the first dose of study drug (Study Day 1) and through the Follow-up Visit should be reported as an adverse event.

Clinically significant abnormal laboratory values or other examinations (e.g., ECG) that are detected at the time of the first dose of study drug (Study Day 1) and worsen during the study should be reported as adverse events. An abnormal laboratory result that is not verified by repeat testing does not necessitate reporting as an adverse event. The Investigator will exercise his or her medical, scientific, and clinical judgment in deciding whether an abnormal laboratory finding or other abnormal assessment is clinically significant. Clinically significant abnormal laboratory values occurring during the clinical study will be followed until repeat tests return to normal,

stabilize, or are no longer clinically significant. Any abnormal test that is determined to be an error does not require reporting as an adverse event.

An overdose is a deliberate or inadvertent administration of a treatment at a dose higher than specified in the protocol and higher than known therapeutic doses. Overdoses with associated symptoms are always handled as AEs and reported as such. Overdoses without associated symptoms are not reported as AEs but are documented in [specify eg, CRF] in order to collate information for the IB regarding the level of excess dosage taken or administered without adverse effects. An overdose will be reported irrespective of outcome even if toxic effects were not observed.

#### 8.1.1 Adverse (Drug) Reaction

For adverse events with a causal relationship to study drug, follow-up by the Investigator will be required until the event or its sequelae resolve or stabilize to a level acceptable to the Investigator.

#### 8.1.2 Unexpected Adverse Drug Reaction

An Unexpected Adverse Drug Reaction is defined as an adverse reaction, the nature or severity of which is not consistent with the applicable product information (see Investigator's Brochure). For gemcabene, the reference safety information is included in [Sections 8.4 and 10](#) of the Investigator's Brochure currently in force. The reference safety information will be reviewed yearly and the periodicity of the review will be harmonized with the reporting period of the Development Safety Update Report.

#### 8.1.3 Assessment of Adverse Events by the Investigator

The Investigator will assess the severity (intensity) of each adverse event as mild, moderate, or severe, and will also categorize each adverse event as to its potential relationship to study drug using the categories of Yes or No, as defined below.

##### Assessment of Severity:

Mild – An event that is easily tolerated and generally not interfering with normal daily activities.

Moderate – An event that is sufficiently discomforting to interfere with normal daily activities.

Severe – An event that is incapacitating with inability to work or perform normal daily activities.

##### Causality Assessment:

The Investigator's assessment of causality must be provided for all AEs. The causality is the determination of whether there exists a reasonable possibility that the study drug itself (eg, gemcabene or placebo) caused or contributed to an AE.

If the final determination of causality is unknown and the Investigator does not know whether the study drug caused the event, then the event will be handled as “related to study drug” for reporting purposes. If the Investigator's causality is “unknown, but not related to study drug”, this should be clearly documented on study records.

The relationship of an adverse event to the administration of the study drug will be assessed according to the following definitions:

**No (unlikely related, unrelated, not related, no relation)** – The time course between the administration of study drug and the occurrence or worsening of the adverse event rules out a causal relationship and another cause (e.g., medical history, concomitant drugs, therapies, and complications) is suspected.

**Yes (possibly related, related)** – The time course between the administration of study drug and the occurrence or worsening of the adverse event is consistent with a causal relationship and no other cause (e.g., medical history, concomitant drugs, therapies, and complications) can be identified.

The definition implies a reasonable possibility of a causal relationship between the event and the study drug. This means that there are facts (evidence) or arguments to suggest a causal relationship.

The following factors should also be considered:

- The temporal sequence from study drug administration -
  - The event should occur after the study drug is given. The length of time from study drug exposure to event should be evaluated in the clinical context of the event.
- Underlying, concomitant diseases (medical history) -
  - Each report should be evaluated in the context of the natural history and course of the disease being treated and any other disease the subject may have.
- Concomitant drug -
  - The other drugs the subject is taking or the treatment the subject receives should be examined to determine whether any of them might be recognized to cause the event in question.
- Known response pattern for this class of study drug -
  - Clinical and/or preclinical data may indicate whether a particular response is likely to be a class effect.
- Exposure to physical and/or mental stresses -
  - The exposure to stress might induce adverse changes in the recipient and provide a logical and better explanation for the event.
- The pharmacology and PKs of the study drug -
  - The known pharmacologic properties (absorption, distribution, metabolism, and excretion) of the study drug should be considered.

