If a subject has more than one TEAE at a given level (eg, SOC and PT), the subject will only be counted once within that level. When summarizing TEAEs by maximum severity or causality, at each level of summarization, subjects who report one or more TEAEs within that level are only counted once at that level using the event of greatest severity (in severity tables) or strongest relationship to study drug (in causality tables). All tables will show the number and percent of subjects with at least one TEAE (or SAE, per the criteria on the table). For example, the table of related SAEs will include a row for number and percent of subjects with at least one related SAE. Additionally, a drug-related TEAE is defined as a TEAE with an assigned relationship of “related.” A listing containing all AEs (pre-treatment and TEAEs) will be created; AEs that are not treatment-emergent will be flagged as non-treatment-emergent. Additionally, a listing containing AEs missing severity or relationship to the study drug will be provided.

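### The Yes and No causality definitions in Protocol 8.1.3 leave two of four cases unclassified, and the Yes definition contradicts the section's own caused-or-contributed standard

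*Protocol*

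**What the plan says.** Protocol 8.1.3 asks the investigator to rate the relationship of each adverse event to study drug "using the categories of Yes or No, as defined below". There is no middle category.

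Under Causality Assessment, the section first states a general test: whether there is a "reasonable possibility that the study drug itself (eg, gemcabene or placebo) caused or contributed to an AE". It then defines the two categories:

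- **Yes**, whose label includes possibly related: the time course fits a causal link and "no other cause (e.g., medical history, concomitant drugs, therapies, and complications) can be identified".
- **No**, whose label includes unlikely related: the time course "rules out a causal relationship and another cause (e.g., medical history, concomitant drugs, therapies, and complications) is suspected".

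The section also has a default. "If the final determination of causality is unknown and the Investigator does not know whether the study drug caused the event", the event is handled as related for the purposes of reporting. An investigator may instead document causality as unknown but not related. After the definitions, the text returns to the idea of a reasonable possibility and lists factors to consider, among them underlying disease and other drugs.

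On the analysis side, SAP 12.1 says that "a drug-related TEAE is defined as a TEAE with an assigned relationship of" related. SAP 9.5 does not impute a missing relationship and leaves such events out of the related-event summaries.

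**The concern.** Each category joins two conditions with an *and*, one on timing and one on another cause. An event that meets one condition of each category belongs to neither. The obvious example is an event with plausible timing in a subject who also has another possible explanation.

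That case is realistic here. Background statin use is allowed and is a stratification factor (Protocol 5.1), and subjects with Type 2 diabetes are enrolled (Protocol 4.1). Myalgia and abnormal kidney function tests are among the most common earlier adverse events (Protocol 1.4). Renal, muscle and liver findings have their own safety sections (Protocol 8.1.4.2 and 8.1.4.3). The Yes definition names medical history and concomitant drugs as causes that defeat a Yes.

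Several things depend on the rating:

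- the tables of related TEAEs, related SAEs and related TEAEs leading to treatment discontinuation (SAP 12.1);
- follow-up until the event resolves or stabilises (Protocol 8.1.1);
- the extra examination, urine and blood tests at the Follow-up Visit, for a subject whose only trigger is an ongoing treatment-related event (Protocol 6.5);
- the SAE reporting timeframe after the 30-day follow-up period (Protocol 8.3);
- expedited reporting, which exempts reactions attributed to background statins or ezetimibe (Protocol 8.5).

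**Working it through.** The plan gives no figure to reproduce, so the check sets the definitions side by side.

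**Step 1. Cross the two conditions.** Inputs: the Yes and No definitions in Protocol 8.1.3.

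| Timing | Other cause | Yes met? | No met? | Category |
|---|---|---|---|---|
| Consistent | None identified | yes | no | Yes |
| Consistent | Identified or suspected | no (other cause) | no (timing) | none |
| Ruled out | None suspected | no (timing) | no (no other cause) | none |
| Ruled out | Suspected | no | yes | No |

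Two of the four combinations have no category. The second row matters most in practice. The third is also a gap: an event that the drug cannot have caused is not a No unless some other cause is suspected.

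**Step 2. Compare the Yes definition with the general test.** The general test is met if the drug contributed. A contributing drug can share the event with another cause, yet the Yes definition fails as soon as another cause is identified. For the second row the general test can therefore give related while the Yes definition does not. The labels add to the conflict: Yes is glossed as including possibly related but demands exclusivity, and No as including unlikely related but demands that timing exclude the drug.

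**Step 3. See whether the default for unknown causality fills the gap.** It covers an investigator who does not know whether the drug caused the event. It does not clearly cover one who suspects both the drug and a statin: that person has a view but no matching category. The default also acts only for reporting. Neither document says that it sets the eCRF relationship field. SAP 12.1 uses the assigned relationship, and SAP 9.5 drops events without one, so an event handled as related for reporting could still be absent from the related tables.

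**Step 4. Consider how many raters face the ambiguity.** The Protocol synopsis plans about 40 to 50 sites for about 90 subjects: 90/50 = 1.8 and 90/40 = 2.25 subjects per site. Many investigators would each rate events from about two subjects, so differences in reading would not even out within a site.

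**The case against.** A reader might infer that muscle and liver events in statin users cannot be rated related at all. The documents do not support that. The general test, the possibly-related label and the later return to a reasonable possibility all support a related rating when a statin is also present. The default makes unknown causality related for reporting. Other drugs appear in the list of factors as something to weigh. A background statin is not automatically an identified cause: Protocol 4.1 requires statins and ezetimibe to have been started at least 12 weeks before screening, and Protocol 4.2 excludes raised CK, raised transaminases, active liver disease and eGFR below 60.

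A reader might also infer that the related-event tables must be too low. That does not follow. The same events fail the No definition just as they fail Yes, so the text forces neither answer.

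The main safety evidence also does not use the rating. Protocol 9.3.2 rests the assessment mainly on the frequency of new or worsening events, laboratory abnormalities and SAEs. SAP 12.1 tabulates all-causality TEAEs and SAEs by arm and by statin use within arm. SAP 12.2, Table 3, applies thresholds to ALT, AST, CK, BUN, creatinine and eGFR. Sites report every SAE whatever its suspected cause (Protocol 8.3). Rating is blinded, and the same wording applies in every arm.

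All of this stands, and it limits the reach of the problem. It does not make the definitions exhaustive, remove the conflict with the general test, or link the default to the eCRF field.

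**Conclusion.** The definitions are wrong as written. They leave two of four combinations unclassified, and the no-other-cause condition contradicts the section's own test. The likely result is inconsistent rating between investigators. Under-attribution to study drug is a risk, because the Yes definition turns on the absence of another identifiable cause, but it is not a certainty.

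The size in events cannot be computed. The documents give no rate for plausibly timed events with another possible cause, and any count would be an assumption. The reach can be stated. Affected are the related-TEAE and related-SAE tables, follow-up tied to treatment-related events, late SAE reporting and expedited reporting. The all-causality adverse event tables and the tables of potentially clinically significant laboratory values are not affected.

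This conclusion assumes that investigators apply the Yes and No definitions as worded. If every site worked from the general test alone, the gap would have little effect, but the rating instruction sends them to the definitions.

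**What to change.** In Protocol 8.1.3, put both categories on the section's own standard:

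- Yes: there is a reasonable possibility that study drug caused or contributed to the event, even if another cause is also possible.
- No: there is no such reasonable possibility.

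Delete the condition that no other cause can be identified and the condition that timing rules out causality. Timing, underlying disease and other drugs remain as factors to weigh.

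State that the default for unknown causality sets the eCRF relationship field, and say how an event documented as unknown but not related is coded. In SAP 12.1, state that the protocol's Yes is what the SAP calls related.

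The cost is wording in the protocol, the eCRF completion guidance and one sentence of the SAP. No new data or visits are needed. The downside is that more events will be rated related, in all arms including placebo, so the related-event tables should be read as comparisons between arms.

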#### 8.1.4 Specific Safety Measures

##### 8.1.4.1 Hemoglobin decrease

For a hemoglobin decrease of  $> 1.5$  g/dL from baseline during the study, repeat hematology studies and reflexive evaluation of reticulocyte count will be performed. The subject's past medical history, concomitant medications (including over the counter drugs and herbal supplements), and any recent symptoms (e.g., bleeding, shortness of breath, fatigue) will be reviewed to determine a potential etiology and make a clinical assessment of the significance of the finding.

##### 8.1.4.2 Creatinine increase

If, at any visit, a creatinine increase of  $> 0.3$  mg/dL (27  $\mu$ mol/L) from baseline, a GFR decrease of  $> 15$  mL/min from baseline, or a  $> 30$  urinary albumin:creatinine ratio mg/g is observed, a repeat chemistry/urinalysis will be performed. The subject's past medical history, concomitant medications (including over the counter drugs and herbal supplements), and any recent symptoms (e.g., fatigue, malaise, polyuria/oliguria, or palpitations) will be reviewed to determine a potential etiology and make a clinical assessment of the significance of the finding.

During the study, clinically significant abnormal results in NGAL will be used as a means of identifying subjects who have unremarkable creatinine/BUN studies at the time of assessment but may require additional or closer/follow-up monitoring of renal parameters. Cystatin-C will be measured at baseline and Week 12.

